# 3.1.1.1 Dose Limiting Toxicity

Dose-limiting toxicity (DLT) is defined as an adverse event that is related (possibly, probably, or definitely) to the administration of CRLX101. DLTs (toxicities occurring within the first 84 days of treatment after the first intravenous infusion of CRLX101) will be defined using the National Cancer Institute (NCI) Common Terminology Criteria for Adverse Events (CTCAE) version 5.0. The following events will be considered DLTs if deemed drug-related:

- Grade ≥3 neutropenia complicated by fever ≥38.5°C (i.e. febrile neutropenia and/or documented infection.
- Grade 4 neutropenia that does not improve within 5 days \*
- Grade 4 thrombocytopenia that does not resolve within 5 days\* or any grade 3-4 thrombocytopenia complicated with hemorrhage;
- Grade 4 anemia that does not resolve within 7 days despite optimal therapy (withholding study drug and red blood cell transfusion);
- Any grade 3-4 non-hematologic toxicity (except fatigue/asthenia < 2 weeks in duration; mucositis in subjects who have not received optimal therapy for mucositis; vomiting or diarrhea lasts less than 72 hours whether treated with an optimal anti-emetic or anti-diarrheal regimen or not; or alkaline phosphatase changes)
- Failure to receive at least 75% of study drug doses during cycle 1 due to toxicity.
- Laboratory results of 3xULN elevation of transaminases and concomitant 2xULN total bilirubin without an alternative etiology
- Any toxicity resulting in greater than two weeks of dose delay.

\*Note: In the event of a Grade 4 neutropenia or thrombocytopenia, a full blood count must be performed no more than 5 days after the onset of the event to determine if a DLT has occurred. The subject will be closely monitored until the resolution to Grade 3 or less.

[figure not shown]

Figure 7: Dosing schema following the lead-in component.

Following the DLT assessment during the lead-in component and validation of the RP2D, participants enrolled thereafter will not participate in the lead-in period. Participants will receive CRLX101 at the RP2D established during the lead-in component via IV infusion on Cycle 1 Day 1 (C1D1). Enzalutamide will be administered orally at a dose of 160 mg once daily beginning on Cycle 1 Day 2 (C1D2), at least 24 hours after the end of the infusion of CRLX101. After the first dose on C1D2, Enzalutamide will be taken once daily for the full duration of the study. Participants will receive CRLX101 at the established RP2D via IV infusion on C1D15 and on Days 1 and 15 of each subsequent cycle.

Following establishment of the RP2D, enrollment on this study will continue until 8 participants are evaluable for the primary endpoint. If 3 or more participants achieve response, then additional participants will be enrolled until a total of 21 participants have been evaluated for the primary endpoint. The accrual ceiling is set for 30 participants, to account for participants that are inevaluable or participants that do not tolerate treatment in the lead-in phase. For more details, refer to Section 8.

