### 3.1.1 Lead-In Component

[figure not shown]

Figure 6: Lead-In Dosing Schema and DLT Assessment

For the first 3 to 6 participants, there will be a lead-in period of two cycles to ensure the safety and tolerability of CRLX101 in combination with enzalutamide. CRLX101 will be started at a dose of 12 mg/m^2, administered via IV infusion on Day 1. Enzalutamide will be administered orally at a dose of 160 mg once daily starting on Day 2 (C1D2) once the 24-hour pharmacokinetic sample timepoint has been collected (at least 24 hours after the end of the CRLX101 infusion). After the first dose on C1D2, Enzalutamide will be taken once daily for the full duration of the study. Participants will receive CRLX101 12 mg/m^2 via IV infusion on Cycle 1 Day 15 (C1D15), Cycle 2 Day 1 (C2D1), and Cycle 2 Day 15 (C2D15). On Cycle 3 Day 1 (C3D1), and Cycle 3 Day 15 (C3D15), CRLX101 will be administered at the previously established MTD (15 mg/m^2 administered via IV infusion). Participants will be assessed from Day 1 to Day 56 (C1D1 to C2D28) for dose limiting toxicities of the CRLX101 12 mg/m^2 dose and from Day 57 to 84 (C3D1 to C3D28) for dose limiting toxicities of the CRLX101 15 mg/m^2 dose (Enzalutamide will be at approximate steady state concentration following Day 29 [C2D1]). Following the DLT assessment period (at the start of Cycle 4), each participant will continue to receive CRLX101 at the participant's specific maximum tolerated dose via IV infusion every 2 weeks (Days 1 and 15) for every subsequent cycle.

For the purposes of this study, re-assessment of the CRLX101 RP2D will be determined based on DLTs deemed likely attributable to CRLX101. DLTs are outlined in Section **3.1.1.1** and the dose modification procedures of CRLX101 are outlined in **3.3.2**. Adverse events deemed attributable to enzalutamide will not influence the on-trial treatment of subsequent participants and will be managed according to the dose modification protocol outlined in Section **3.3.3**. Final determination of the drug attributable to an adverse event is at the discretion of the Principal Investigator or designee.

If none of the three participants experience a dose limiting toxicity during the lead-in phase (Day 1-84), subsequent participants enrolled on trial with receive CRLX101 at a dose of 15 mg/m^2 via IV infusion every 2 weeks.

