### 3.3 Dose Modifications

- 3.3.1 General Rules for Dosing Delays/Dose Modifications and Management of Toxicities
  - In the case of toxicity, appropriate medical treatment should be used (including antiemetics, anti-diarrheals, etc.).
  - Once a participant has a dose reduction for toxicity, the dose will not be increased.
  - A maximum of two dose reductions are permitted
  - If either agent is discontinued due to toxicity, the participant may continue on the other agent.
  - Participants continuing to experience toxicity at the off-treatment visit will be contacted for additional assessments until the toxicity has resolved or is deemed irreversible. When logistically feasible, willing participants will remain on the study to have additional assessments.
  - For AEs that are unrelated to the study drugs, dose may be held for up to 28 days at the discretion of the Principal Investigator or designee.
  - The associate investigator and/or PI will determine whether one or both drugs are responsible for an observed toxicity and will manage that toxicity as described below.

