# 3.3.2.2.1 Neutropenia

In the lead-in stage, subjects will not receive growth factors prior to C1D1 and prophylactic use of growth factors is prohibited during the first 3 cycles (Days 1-84) or until neutropenia is identified as a DLT (at discretion of the Principal Investigator or designee), whichever comes first. Growth factors can be used during a drug hold to assist the recovery and in subsequent cycles after a drug hold. Please note that G-CSF should not be used within at least 24 hours of the last dose of CRLX101 treatment.

In the Phase 2 stage, subjects may receive growth factors prophylactically at the discretion of the Principal Investigator or designee.

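### The lead-in can clear 15 mg/m² on participants who never received it or were observed at it for less than 28 days, because the DLT window runs by calendar and no exposure is required

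*Combined protocol and SAP*

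**What the plan says.** All references are to the combined protocol and SAP.

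**Window.** Section 3.1.1.1 defines DLTs by calendar time: "DLTs (toxicities occurring within the first 84 days of treatment after the first intravenous infusion of CRLX101". The clearing rule in 3.1.1 does the same: "If none of the three participants experience a dose limiting toxicity during the lead-in phase (Day 1-84", after which later participants receive 15 mg/m². One DLT in three brings three more participants, and one in six also clears the dose. Section 3.1.1 also ties the 15 mg/m² assessment to cycle days, "from Day 57 to 84 (C3D1 to C3D28) for dose limiting toxicities", and ends it by cycle: "Following the DLT assessment period (at the start of Cycle 4". Section 3.3.2.2.1 again treats the two as the same: "prophylactic use of growth factors is prohibited during the first 3 cycles (Days 1-84".

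**Delays.** One type of drug-related delay is itself a DLT: "Any toxicity resulting in greater than two weeks of dose delay". Other delays are allowed. For unrelated adverse events the "dose may be held for up to 28 days at the discretion of the Principal Investigator or designee" (3.3.1). Section 4.2.2 stops CRLX101 at least 3 days before palliative radiation and restarts it 14 to 21 days after. Table 3 delays doses for cytopenias. Under 14.1.6 a delayed dose moves the next one to two weeks later.

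**Reductions.** Section 3.3.1: "Once a participant has a dose reduction for toxicity, the dose will not be increased".

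**Evaluability.** Section 10.2 defines it for safety (one dose) and for efficacy, but not for DLT. Section 10.4.3 checks the DLT count among participants enrolled in the lead-in.

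**The concern.** The lead-in exists to confirm 15 mg/m² with enzalutamide before up to 21 further participants start at that dose. Cycle 3 is the only period in which the DLT rule sees that dose in combination. Two things weaken it.

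First, the calendar window closes on Day 84 however late the first 15 mg/m² infusion was given. A real toxicity at 15 mg/m² after Day 84 would not be a DLT under 3.1.1.1, although it would fall inside Cycle 3.

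Second, the rule counts participants without a DLT. It does not ask whether they received the dose being cleared, and choosing one window over the other does not cure this. A participant who never reached 15 mg/m² adds to the denominator and cannot add a 15 mg/m² DLT to the numerator, which pushes the decision towards clearance.

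**Working it through.** **1. The plan's own window.** With 28-day cycles, C3D1 = 2 × 28 + 1 = Day 57 and C3D28 = 3 × 28 = Day 84. The stated equivalence is reproduced with no delay.

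**2. Effect of delay, calendar wording.** Let d be the cumulative non-DLT delay before C3D1. The 15 mg/m² infusions fall on Days 57 + d and 71 + d, and 28 − d days are observed by Day 84.

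| d (days) | First infusion | Second infusion | 15 mg/m² doses by Day 84 | Days observed |
|---|---|---|---|---|
| 0 | 57 | 71 | 2 | 28 |
| 7 | 64 | 78 | 2 | 21 |
| 14 | 71 | 85 | 1 | 14 |
| 21 | 78 | 92 | 1 | 7 |
| 28 | 85 | 99 | 0 | 0 |

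One drug-related delay can cost at most 14 days without being a DLT. Single-fraction radiation t days after an infusion (t = 3 to 14) allows restart at t + 14 to t + 21, against a dose due at day 14. The delay is therefore t to t + 7, or 3 to 21 days. On the cycle reading, delay removes no exposure: at d = 28, C3D28 is Day 112.

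**3. Routes to no exposure on either reading.**
- Progression: scans are due by C3D1 (3.4, Table 6 footnotes), and progressive disease ends therapy (3.6.1).
- Reduction: Grade 4 thrombocytopenia that resolves within 5 days without hemorrhage is not a DLT (3.1.1.1). Table 3 still requires a reduction, and 3.3.1 bars a later increase.

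**4. Effect on clearance.** Let p be the 28-day DLT probability at 15 mg/m². Assume independent participants, no DLT at 12 mg/m², and full exposure of any expansion three. The documents give no value for p, so 0.33 and 0.20 are illustrative.
- All exposed: (1 − p)³ + 3p(1 − p)² × (1 − p)³. At p = 0.33: 0.301 + 0.134 = 0.434. At p = 0.20: 0.709.
- One of the first three unexposed: (1 − p)² + 2p(1 − p) × (1 − p)³. At p = 0.33: 0.449 + 0.133 = 0.582. At p = 0.20: 0.804.
- One of the first three at d = 14 on the calendar wording, with constant hazard, so that his risk is 1 − √(1 − p) (0.181 at p = 0.33): 0.367 + 0.133 = 0.501. At p = 0.20: 0.754.

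**5. How often someone leaves before 15 mg/m².** Section 10.2 gives a lower PFS quartile of 3 months in each benchmark group. Day 56 is 56/30.4375 = 1.84 months. Under constant hazard, 1 − 0.75^(1.84/3) = 0.162 progress by then. Section 6.3.3.3 lets some with new bone lesions at first restaging continue as possible flare; if half do (an assumption), 0.081 leave. At least one of three is then unexposed with probability 1 − 0.919³ = 0.22 to 1 − 0.838³ = 0.41.

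**The case against.** The strongest reply is that the intent is plain. Section 3.1.1 schedules 15 mg/m² on C3D1 and C3D15 and describes the later window as assessing that dose, so nobody would count an unexposed participant. Section 10.4.3 looks at the toxicity data as well as the DLT count, 7.4.1 provides weekly review, and 10.4.6 requires a safety evaluation before efficacy enrollment. Section 10.2 caps evaluable lead-in participants at 6, so evaluability was contemplated. Figure 6 and the decision figure were not in the text available for review and might settle the window.

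Part of this stands. The intent is clear and the reviews might catch the problem. But none of the readable text sets an exposure requirement, and 10.4.3 counts those enrolled. The point is therefore limited to the text shown.

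The reduction route is narrow. Table 4's exceptions match the DLT exceptions, so drug-related Grade 3–4 non-hematologic reductions are generally DLTs already. Table 3 applies at 12 mg/m² only after Cycle 1. In monotherapy at 15 mg/m² every two weeks, treatment-related neutropenia occurred in 5 of 44 participants in one study, and Grade 3 or higher neutropenia in 2 of 97 in another (1.2.5.7.1).

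A reader might infer that ordinary delays could remove 15 mg/m² exposure altogether. The documents do not support that: it needs d ≥ 28, meaning a full 28-day unrelated hold or accumulated delays, and only on the calendar reading.

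A reader might also take the 4-month median PFS as exponential and conclude that 27% progress by Day 56, so that 62% of lead-ins lose at least one of three. That model puts the lower quartile at 4 × ln 0.75 / ln 0.5 = 1.66 months, against the 3 months reported. A 3-month quartile with a 4-month median implies rising hazard, so 16% is more likely high than low.

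**Conclusion.** The concern holds as a gap in the decision rule. Following the text as written can leave a 15 mg/m² toxicity out of the DLT count, or count as DLT-free someone who never received that dose. One unexposed participant among the first three raises the chance of clearance from 43% to 58% at an assumed 33% DLT rate, and from 71% to 80% at 20%. Loss of at least one of the first three before 15 mg/m² is plausible in about 22–41% of lead-ins. That range rests on a benchmark from third- and fourth-line patients on other drugs, constant hazard, and an assumed flare allowance. No delay rate is given, so the frequency of shortened windows is not estimated.

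It would be too strong to infer that 15 mg/m² is likely to be cleared with nobody exposed. If 16.2% leave early, all three do so with probability 0.162³ = 0.4%. Harm is also bounded: 15 mg/m² every two weeks is the monotherapy MTD (1.2.5.4), and dose reductions apply to later participants. The change should be made, but the point does not undermine the trial as a whole.

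**What to change.** In 3.1.1, 3.1.1.1 and 10.2:
- Run the 15 mg/m² window for 28 days from the actual first 15 mg/m² infusion, or until 14 days after the second if that is later.
- Run the 12 mg/m² window from C1D1 to the first 15 mg/m² infusion or, for a participant never escalated, to a fixed end such as 28 days after the last 12 mg/m² dose.
- Count a participant as DLT-free at 15 mg/m² only if both infusions were received and the window was completed. Replace those who miss this for reasons other than CRLX101 toxicity.
- Do not count as DLT-free anyone kept from 15 mg/m² by CRLX101-related toxicity, and report each such case at the RP2D decision.
- State the lead-in ceiling as 6 DLT-evaluable participants, in line with the evaluable wording in 10.2, in place of the accrual ceiling of 6 in 3.1.1 and 10.2. Keep the overall ceiling of 30.

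The text change is a few sentences. The go decision moves by the length of any delay, and by at least 84 days plus enrollment time if someone is replaced after the others finish. With 8–16% leaving early, 3 evaluable participants need 3/0.919 = 3.3 to 3/0.838 = 3.6 enrolled, and 6 need 6.5 to 7.2. Spare places are 30 − 21 − 3 = 6 if the lead-in stops at three and 30 − 21 − 6 = 3 if it expands. They are shared with inevaluable two-stage participants.

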### 3.2 Drug Administration

## 3.2.1 CRLX101

CRLX101 will be diluted with 5% dextrose for injection (D5W) to a total volume of 500 mL and should be infused intravenously over 60-75 minutes (See 13.1). Nothing else should be added to the bag.

The CRLX101 infusion should begin immediately after preparation and diluted CRLX101 infusion solution not used within 6 hours should be destroyed following institutional practices.

Hypersensitivity reaction (HSR) have been observed in a small number of subjects treated with CRLX101. Most HSR associated with CRLX101 are mild and moderate, reversible upon study drug interruption. In general, subjects restarted CRLX101 infusion at a slower infusion rate without recurrence. In addition to the mandatory premedication to prevent HSR, the duration of CRLX101 infusion must be prolonged from 1 hour to 2 hours (+/- 10 minutes) in participants who have experienced a previous infusion-related reaction.

3.2.1.1 Hydration and Premedication Prior to CRLX101 Treatment

Subjects will receive IV hydration infused approximately over two hours with up to 1,000 mL of 0.9% sodium chloride solution before and after the administration of CRLX101 to reduce risk of cystitis adverse reaction. The administration rate and volume should follow standard site procedures and may be adjusted by the Principal Investigator or designee based on patient-specific factors. Participants should be encouraged to adequately hydrate throughout the cycle, especially during the first 48 hours following the infusion of CRLX101.

Subjects should be pre-medicated with the following drug classes 30-90 minutes prior to start of CRLX101 infusion to reduce likelihood of hypersensitivity adverse reactions:

- a corticosteroid (dexamethasone 20 mg IV or PO)
- an antihistamine (diphenhydramine 50 mg IV or PO)
- an H2 antagonist (famotidine 20 mg IV or PO; 30-60 minutes prior to start of CRLX101)
- an anti-emetic, (e.g., a 5-HT3 receptor antagonist)

At the discretion of the Principal Investigator or designee, a 650 mg dose of Acetaminophen PO may also be given.

The drug recommendations can be adjusted per local institutional guidelines with approval from the Principal Investigator or designee.

The example medications, route of administration, and dose indicated should be the medication-of-choice if clinically feasible. It is acknowledged that the premedication regimen may be altered for participant safety during the study (for example, if a participant experiences a hypersensitivity/infusion reaction related to study drug, the premedication regimen may be altered for subsequent cycle dosing based on the Principal Investigator or designee's discretion).

3.2.1.2 Sodium Bicarbonate Administration with CRLX101 Treatment

Participants will undergo an experimental urine alkalinization protocol in addition to IV hydration on C2D15 (See Section 5.1.1.2). Participants will receive sodium bicarbonate orally pre- and post-CRLX101 infusion on C2D15. Details about recommended dosing are outlined below (Table 1) and in Section 5.1.1. All other doses of CRLX101 will be given with IV hydration as described above. At the discretion of the Principal Investigator or designee, the strength, frequency, and/or schedule of oral sodium bicarbonate dosing may be modified on a participant by participant basis.

Table 1: Recommended Oral Alkalinization Pre- and Post-CRLX101 Infusion

Timing	Dose, route, and frequency
--------	----------------------------

Starting from 48 hours prior to CRLX101 infusion	Take sodium bicarbonate by mouth, 650mg x2, 4 times a day (QID), for two days before CRLX101 infusion
On the day of CRLX101 infusion	Take sodium bicarbonate by mouth, 650mg x2, 4 times a day (QID), for one day
After CRLX101 infusion	Take sodium bicarbonate by mouth, 650mg x2, 4 times a day (QID), for one day after CRLX101 infusion

At the discretion of Principal Investigator or designee, participants who are prone, or likely, to develop cystitis may be recommended to receive either oral or intravenous sodium bicarbonate pre and/or post CRLX101 administration.

## 3.2.2 Enzalutamide

All participants will receive enzalutamide 160 mg orally, daily starting cycle 1 day 2 (C1D2). Enzalutamide may be administered with or without food. It is recommended that enzalutamide be administered daily in the evenings, however, daily administration time of enzalutamide is based on participant preference.

### 3.3 Dose Modifications

- 3.3.1 General Rules for Dosing Delays/Dose Modifications and Management of Toxicities
  - In the case of toxicity, appropriate medical treatment should be used (including antiemetics, anti-diarrheals, etc.).
  - Once a participant has a dose reduction for toxicity, the dose will not be increased.
  - A maximum of two dose reductions are permitted
  - If either agent is discontinued due to toxicity, the participant may continue on the other agent.
  - Participants continuing to experience toxicity at the off-treatment visit will be contacted for additional assessments until the toxicity has resolved or is deemed irreversible. When logistically feasible, willing participants will remain on the study to have additional assessments.
  - For AEs that are unrelated to the study drugs, dose may be held for up to 28 days at the discretion of the Principal Investigator or designee.
  - The associate investigator and/or PI will determine whether one or both drugs are responsible for an observed toxicity and will manage that toxicity as described below.

## 3.3.2 CRLX101 Dose Modification

### 3.3.2.1 General Recommendations

The lead-in dosing schema is designed to ensure against significant drug-drug interactions between CRLX101 and enzalutamide. If dose modifications are necessary, the general approach to dose modification is listed in Table 2. Such dose modifications should be followed according to the dose level in which the participant experiences an undesirable adverse event (See Section

**3.1.1** for Lead-in schema rules). Adverse events should be treated with the appropriate maximum intervention and dose reductions should be clearly documented in participant notes.

# Table 2: Guidelines for CRLX101 Dosing Reductions

	CRLX101 Dosage Schedule						
	Initial Dosing	First dose reduction	Second dose reduction				
Dose Level 1	12 mg/m 	9 mg/m 	6 mg/m 				
Dose Level 2	15 mg/m 	$12 \text{ mg/m}^2$	9 mg/m 				

3.3.2.2 CRLX101-Related Hematologic Toxicities

Table 3: Dose Modification and Management of Hematologic Adverse Events (CRLX101)

Cycle Day	Grade or count (cells/mm  )	Dose Delay or Reduction for Hematological Toxicity (Phase 2 stage and after Cycle 1 of a new dose level in lead-in stage)				
Neutrop	enia					
1 or 15	Grade 2 (<1500)	
 
For first neutropenic eventa, delay CRLX101 dose until ≤ Grade 1, resume CRLX101 with no dose change
 
				
		• For second neutropenic event a , delay CRLX101 until ≤ Grade 1, resume CRLX101 with no dose change, add G-CSF b support				
		
 
For third neutropenic eventa, delay dose until ≤ Grade 1, resume CRLX101 with the dose reduced by one dose level, continue G- CSFb support
 
				
	$\geq$ Grade 3 (<1000)	
 
For first neutropenic eventa, delay CRLX101 dose until ≤ Grade 1, resume CRLX101 with no dose change, add G-CSFb support
 
				
		• For second neutropenic event a , delay CRLX101 until ≤ Grade 1, resume CRLX101 with dose reduced by one dose level, continue G-CSF b support				
		• For third neutropenic event a , delay dose until ≤ Grade 1, resume CRLX101 with the dose reduced by one further dose level, continue G-CSF b support				
Thromb	ocytopenia					
1 or 15	<100,000	• Delay CRLX101 dose until $\geq$ 100,000				

Cycle Day	Grade or count (cells/mm  )	Dose Delay or Reduction for Hematological Toxicity (Phase 2 stage and after Cycle 1 of a new dose level in lead-in stage)							
		• Resume CRLX101 with no dose change							
	Grade 2 (<75,000) and Grade 3 (<50,000)	
 
Delay dose forCRLX101 until ≥ 100,000
 
Resume CRLX101 with no dose change (the dose may be reduced one dose level or kept at the same dose at the discretion of the Principal Investigator or designee)
 
							
		
 
if grade 2 or grade 3 recurs,
 
Hold dose for CRLX101 until ≥ 100,000
 
Resume CRLX101 with dose reduced by one dose level
 
							
	Grade 4	
 
Hold dose for CRLX101 until ≥ 100,000
 
Resume CRLX101 with dose reduced by one dose level
 
Do not make up missing dose
 
							
Anemia									
1 or 15	≥ Grade 3 (<8g/dL)	
 
Delay dose for CRLX101, and consider RBC transfusion(s) based on clinical criteria
 
After improved to ≤ Grade 2, resume CRLX101 with no dose change (the dose may be reduced one dose level or kept at the same dose at the discretion of the Principal Investigator or designee)
 
Consider EPO support per guidelines
 
If Grade 3 recurs,
 
Delay dose for CRLX101, and consider RBC transfusion(s) based on clinical criteria
 
After improved to ≤ Grade 2, resume CRLX101 with dose reduced by one dose level
 
Consider EPO support per guidelines
 
							

Cycle Day	Grade or count (cells/mm  )	Dose Delay or Reduction for Hematological Toxicity (Phase 2 stage and after Cycle 1 of a new dose level in lead-in stage)
	Grade 4	• Delay dose for CRLX101, and consider RBC transfusion(s) based on clinical criteria
		• After improved to ≤ Grade 2, resume CRLX101 with dose reduced by one dose level
		• Consider EPO support per guidelines.

a A neutropenic event is defined as  $\geq$  Grade 2 neutropenia on D1 or  $\geq$  Grade 3 neutropenia on Day 15

b G-CSF (filgrastim or equivalent, pegfilgrastim is also permitted) should not start until at least 24 hours after discontinuation of chemotherapy. Discontinue G-CSF once ANC is  $\geq$ 1000/mm^3. Wait at least 24 hours after G-CSF is discontinued before resuming chemotherapy.

- Treatment may be delayed for a maximum of 28 days after holding the treatment for toxicities that develop and do not resolve as defined above (exemptions: lymphopenia, or leukopenia in the absence of grade 3 or higher neutropenia).
- Bi-weekly blood counts will be obtained throughout the study. If any evaluation demonstrates grade ≥ 3 neutropenia or grade ≥ 2 thrombocytopenia, a repeat hematology assessment will be obtained 2-4 days later.
- Management of prolonged hematological toxicities while on study treatment

If a participant develops prolonged hematological toxicity such as:

- ≥2 week interruption/delay in study treatment due to CTC grade 3 or worse anemia and/or development of blood transfusion dependence
- ≥3 week interruption/delay in study treatment due to CTC grade 3 or worse neutropenia (ANC < 1 x 109/L)
- $\geq$ 3 week interruption/delay in study treatment due to CTC grade 3 or worse thrombocytopenia (Platelets < 50 x 109/L)

Weekly differential blood counts including reticulocytes (calculate reticulocyte index (RI), RI = reticulocyte count x hematocrit (Hct)/normal Hct; a value of 45 is usually used for normal Hct) and peripheral blood smear could be considered (may be done at an outside facility). If any blood parameters remain clinically abnormal after 4 weeks further investigations could be considered including hematology evaluation. Bone marrow analysis and/or blood cytogenic analysis could be considered at this stage according to standard hematological practice.

Development of a confirmed myelodysplastic syndrome or other clonal blood disorder should be reported as an SAE. Study treatment should be discontinued if diagnosis of myelodysplastic syndrome is confirmed.

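### Table 3's Grade 2 neutropenia row calls for G-CSF at counts where footnote b already says to stop it, and Section 3.3.2.2.1 does not settle which governs

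*Combined protocol and SAP*

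**What the plan says.** All the relevant text is in Section 3.3.2.2 (Table 3 and its footnotes) and Section 3.3.2.2.1.

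- **Grade limits.** Table 3 has a Grade 2 neutropenia row (ANC below 1500/mm³) and a row for Grade 3 or worse (below 1000/mm³). The text after the table repeats the second limit: "CTC grade 3 or worse neutropenia (ANC < 1 x 109/L" (the exponent of 10⁹ was flattened in extraction).
- **Grade 2 row.** The first event brings a delay only. At the second, after recovery to Grade 1 or better, the site is to "resume CRLX101 with no dose change, add G-CSF" support. At the third, CRLX101 resumes one dose level lower and G-CSF support continues.
- **Footnote a.** It opens "A neutropenic event is defined as" and counts Grade 2 or worse on Day 1, but only Grade 3 or worse on Day 15.
- **Footnote b**, attached to each mention of G-CSF. G-CSF "should not start until at least 24 hours after discontinuation of chemotherapy". Then: "Discontinue G-CSF once ANC is" at or above 1000/mm³. At least 24 hours must pass between the end of G-CSF and the next chemotherapy.
- **Section 3.3.2.2.1.** In the paragraph on the lead-in stage: "Growth factors can be used during a drug hold to assist the recovery and in subsequent cycles after a drug hold". Then: "In the Phase 2 stage, subjects may receive growth factors prophylactically at the discretion of the Principal Investigator or designee". Neither sentence mentions an ANC at which use stops.

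**The concern.** In the Grade 2 row, G-CSF is the only measure between a simple delay and a dose reduction, and the third-event instruction to continue it presumes that it was started at the second. The stop count in footnote b is the lower boundary of Grade 2 itself. A site treating a second Grade 2 event therefore has one line telling it to add G-CSF and another telling it to stop at the count the participant already has.

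What is at stake is consistency of management. Two participants with the same counts could be handled differently, one receiving G-CSF before a dose reduction and one not, depending on which line is followed. Any resulting difference in later counts could carry through to the length of holds, the CRLX101 dose received and the safety summary. Length of hold matters in its own right, because Section 3.6.1 removes a participant from the causative drug after a toxicity delay of more than 28 days.

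**Working it through.** No sample-size, power or alpha figure is involved. The check compares the stated thresholds.

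**1. Ranges implied by Table 3.**
- Grade 2: below 1500 but not below 1000, so 1000 to <1500/mm³.
- Grade 3 or worse: below 1000/mm³. The second statement of this limit agrees: 1 × 10⁹/L ÷ 10⁶ mm³/L = 1000/mm³.
- Resumption (Grade 1 or better): not below 1500/mm³.

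**2. Share of each range that already meets footnote b's stop condition (ANC ≥1000), counting whole-number values.**

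| State | ANC range (/mm³) | Values meeting the stop condition |
|---|---|---|
| Grade 2 event | 1000–1499 | 500 of 500 (100%) |
| Grade 3 or worse event | 0–999 | 0 of 1000 (0%) |
| Resumption | 1500 and above (checked to 3000) | 1501 of 1501 (100%) |

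**3. The Grade 2 row in sequence.** At a second Day 1 event the ANC is 1000–1499, so the stop condition is met. During the hold it remains met unless the ANC falls below 1000. At resumption the ANC is at least 1500, so it is met again. It is unmet only if the ANC later drops below 1000.

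**4. Two readings of footnote b.**
- *Literal:* no G-CSF while the ANC is ≥1000. The delay and the same-dose resumption can be done, but the G-CSF part of the step has no window unless the count falls into the Grade 3 range.
- *Sequential:* G-CSF starts at least 24 hours after the infusion and stops when the ANC has recovered to 1000 after a later fall. The step can then be done. Applying the stop would need counts between visits. The study calendar (Table 6) lists blood counts on Days 1 and 15. The text after Table 3 requires a repeat at 2–4 days only after Grade 3 or worse neutropenia (or Grade 2 or worse thrombocytopenia). It also mentions bi-weekly counts, which can mean twice a week or every two weeks.

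**5. The reduction that follows at the third event (Table 2, first reduction).** (15 − 12)/15 = 20%; (12 − 9)/12 = 25%.

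**6. Frequency.** Section 1.2.5.7.1 reports treatment-related neutropenia in 5 of 44 participants (11%) on single-agent CRLX101 15 mg/m² every two weeks. If that rate carried over (an assumption), 5/44 × 21 ≈ 2.4 of 21 participants would have neutropenia reported. The Grade 2 share, the rate of second and third Day 1 events and the rate in combination with enzalutamide are not given, so the number affected cannot be estimated.

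**The case against.** The strongest reply is that footnote b is a stop rule, not a bar on starting. Read in order, it covers support around an infusion: a start time, a stopping count, then a gap before the next dose. Table 3 attaches G-CSF to the resumed treatment, and Section 3.3.2.2.1 expressly allows growth factors after a hold and prophylactically in the Phase 2 stage with no count attached. The literal reading would also rule out G-CSF given after resumption in the Grade 3 or worse row, and any prophylaxis begun at a normal count, which suggests that it was not intended.

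Much of this stands. A reader might infer that the second-event step cannot be carried out at all. The documents do not support that: the delay and same-dose resumption are unaffected, and under the sequential reading G-CSF can be given too. What the reply does not do is find that reading in the text. Section 3.3.2.2.1 grants permission without saying whether the 1000/mm³ stop applies. During a hold for a Grade 2 count, it allows what footnote b, taken literally, has already ended.

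The reply is also right on scope. Although the row is labelled for Day 1 or Day 15, footnote a makes Grade 2 an event only on Day 1, and G-CSF enters this row only at the second event.

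**Conclusion.** The Grade 2 row, footnote b and Section 3.3.2.2.1 are not consistent on G-CSF at an ANC of 1000/mm³ or more. The conflict covers the whole Grade 2 range and every resumption count, and touches two of the row's three steps. Under the literal reading a participant could lose a dose level at the third event without the G-CSF step that precedes it; under the sequential reading this need not happen. The text does not choose between them. This rests on taking the grade limits from Table 3 itself. It takes no view on which clinical rule is right.

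Two further inferences are tempting and do not hold.
- In the Grade 3 or worse row, G-CSF stops at 1000 while CRLX101 waits for 1500. That is not a contradiction: these are different actions, both rules can be followed, and nothing says that G-CSF must carry the count to 1500.
- A reader might conclude that the test of activity at the RP2D is compromised. The delay and reduction rules are the same under either reading, so any effect would be indirect, through later counts, and the documents give nothing to size it with.

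The two-stage design's sample sizes, decision limits and error rates are unaffected. The point is worth correcting because it bears on safety management and dose received, and because the correction is cheap.

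**What to change.** Amend Table 3, footnote b and Section 3.3.2.2.1 together so that:

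1. the counts that start G-CSF and the count that stops it are compatible for a Grade 2 event;
2. support is defined as treatment during the hold, cover after the resumed infusion, or both;
3. the text states whether the footnote b stop applies to the later-cycle and prophylactic use allowed in Section 3.3.2.2.1.

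The Day 1 or 15 label on the Grade 2 row can be aligned with footnote a in the same edit. The clinical team decides what the rule should be.

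The cost is table, footnote and section wording in an amendment. No extra participants are needed, and no extra visits or blood counts unless the rule the clinical team chooses calls for them.
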